13.3 Retention and Availability of Records

The Sponsor-Investigator/ Principal Investigator will maintain records in accordance with standards of Good Clinical Practice, and applicable local institutional policies and procedures. IND records and reports will be retained for a minimum of 2 years after study discontinuation, or the FDA has been formally notified (21 CFR 312.57). Participants provide consent to authorization for the use of private health information. Therefore, all research records, including signed consent forms and data/case report forms (source documents) will be retained for at least seven, (7) years beyond the close of the study.

The Sponsor-Investigator/ Principal Investigator will make study data and research records available for audit purposes and inspections if so requested by authorized representatives of Washington University Institutional Review Board, the Human Research Protection Office or Regulatory Agencies, i.e., Food and Drug Administration or National Institutes of Health, the source of grant funding.

13.3.1 Archival of Imaging Data

Only code numbers will appear on any data and documents to be used for evaluation or statistical analysis. Publications emanating from this research will not identify individual patients. HIPAA compliance will be enforced as per Washington University policy and HRPO approval.

Processed and raw PET/CT data will be transferred to the Central Neuroimaging Data Archive (CNDA). Request for access to CNDA must be reviewed and approved by the Principal Investigator or an engaged sub-investigator. Data access is limited to approved user roles as well as assigned access privileges. CNDA complies with Section 164.310 of the Health Information Portability and Accountability Act (HIPAA) that specifies physical safeguards that are required for protection of Electronic Protected Health Information (EPCI) to avoid unauthorized disclosure, modification, or destruction. The CNDA system has the functionality to create audit tables used to monitor traffic through the system and to identify unauthorized attempts to upload or change information or otherwise cause damage.

14 PROTECTIONS, RIGHTS, AND CONFIDENTIALITY

14.1 Informed Consent

The informed consent process will occur in accordance with the Declaration of Helsinki, ICH GCP, U.S. Code of Federal Regulations for Protection of Human Subjects (21 CFR 50.25[a,b], CFR 50.27, and CFR Part 56, Subpart A), the Health Insurance Portability and Accountability Act (HIPAA), and applicable institutional research policies and procedures.

Written informed consent will be obtained from each research participant prior to the initiation of any research procedure. All participants will be given ample opportunity to review the informed consent form to consider participation in the study, under circumstances that would eliminate undue influence, and time to discuss with family and the research team. Participants will be informed of the right to refuse to participate that will not involve a penalty or loss of benefits. A participant may withdraw from study participation at any time without interfering with routine clinical care. The informed consent process will take place in a private area. The Investigator or designee will review the consent form with the participant, confirm eligibility criteria and assess the participants' level of understanding. The informed consent process shall be documented, and a copy of the consent will be provided to the participant.

14.2 Confidentiality

See the [Data Archiving](#) section for details. All data are safeguarded in accordance with the Health Insurance Portability and Accountability Act (HIPAA) and by the principles and practices of strict confidentiality. Protected Health Information (PHI) on study participants will be managed according to Washington University Policies and Security Requirements. Studies are done for research purposes only. Reports from patients' records concerning research observations will not be available to outside medical facilities without written consent of the participant. Participants will be given the contact information for the University's Privacy Officer for questions or concerns about privacy and the use of PHI.

Electronic data obtained as part of the research project will be stored on a secure network with password access. Hardcopy data will be stored in a 2-tiered locked system. The research team will

follow state and federal laws. The research team will obtain consent to use and share the subject's information. When possible, the research team will de-identify information that could be linked to the subject.

Participant study related electronic data may be saved to Box, a HIPAA compliant cloud-based file storage and collaboration tool that allows for file sharing. Any electronic data saved to local computers are encrypted, password-protected with limited access. Participant hardcopy data (e.g., participant signed consent forms) will be stored under a 2-tiered locked system with limited access to only research team members.

14.2.1 Certificate of Confidentiality

To further protect the privacy of study participants, a Certificate of Confidentiality (CoC) will be issued by the National Institutes of Health (NIH). This certificate protects identifiable research information from forced disclosure of research participants. It allows the investigator and study team members or others who have access to research records to refuse to disclose identifying information on research participants in any civil, criminal, administrative, legislative, or other proceedings, regardless of the type of whether at the federal, state, or local level.

14.3 Data Protection

Participants will be assigned a unique research ID code for the research study. Imaging scans and the data and study documents produced as a result of the research and used for evaluation or statistical analysis are labeled with the ID code and the date of the scan.

Publications emanating from this research will not identify individual participants. Reports from patients' records concerning research observations will not be available to outside medical facilities without the written consent of the participant.

14.4 Data Security

Informed consent will be obtained to use and share information. When possible, the research team will de-identify information that could be linked to the participant. Signed hard copy consent forms will be stored in a 2-tiered locked system with limited access to research team members.

14.5 Future Use of Data/ Data Sharing

Important elements for data sharing are included in the consent form and are discussed during the informed consent process. All data is coded and linked with the subject's unique identifier. Information generated by this study, including data and stored blood samples, if applicable will be to be used now and in the future to address research questions in similar fields or other unrelated areas. Research investigators may be at Washington University or outside the university at other research centers, institutions, or industry sponsor of the research.

Coded study data will be maintained at Washington University. This coded data may also be shared with other investigators doing research in similar fields. These investigators may be at Washington University or other research institutions. We may also share coded data with large repositories for broad sharing with the research community. If the participant's research data is placed in one of these repositories, only qualified researchers who have received prior approval from individuals that monitor the use of the data will be able to look at this information.

15 ETHICAL AND FINANCIAL CONSIDERATIONS

15.1 Washington University Institutional Review Board

This imaging study will be conducted in compliance with the protocol approved by Washington University Institutional Review Board, the Human Research Protection Office (HRPO) and in accordance with state and federal government regulations standards of Good Clinical Practice, and applicable institutional research policies and procedures.

The Sponsor-Investigator/ Principal Investigator agrees the study will not be initiated prior FDA correspondence to proceed and not before receipt of IRB or other required regulatory committee approvals. The protocol and informed consent form will be reviewed and approved by IRB/HRPO and the Radioactive Research Drug Committee (RDRC) at Washington University. All subsequent amendments will be submitted to IRB/HRPO and if applicable, the RDRC for approval and other applicable committees as needed.

Washington University complies with the regulations outlined in 45 CFR 46, 21 CFR 50, and 21 CFR 56. The Association for the Accreditation of Human Research Protection Programs has accredited the Institutional Human Research Protection Program since 2004. WU HRPO has two duly appointed IRBs established and is registered in accordance with 45 CFR 46.107, 21 CFR 56.106, and 21 CFR 56.107.

15.2 Funding Source

The U.S. National Institutes of Health is funding this imaging study.

15.3 Conflict of Interest

The Sponsor-Investigator, Principal Investigator, and Sub-Investigators of the research team will follow applicable University Conflict of Interest policies statements as required under Part 54 of Title 21 of the CFR. All members of the research team will verify their financial interests related to the study. The Sponsor-Investigator will promptly report any changes to financial disclosure information according to institutional policies and FDA guidelines for financial interest under 21 CFR 312.57b and 312.64.

15.4 Participant Compensation

Research participants are compensated for their time, research-related inconveniences and discomforts experienced during the study. Any expenses incurred in reimbursing participants are for reasonable and customary medical costs incurred related to the treatment of an adverse event experienced that is determined, in consultation with the Sponsor-Investigator/Principal Investigator, was reasonably related to the administration of the investigational radiotracer, ⁶⁸Ga-Galmydar.

16 ATTACHMENTS

The Schedule of Activities (SoA) tables for each group begins on the next page, see [Table 2 for the Dosimetry group](#) and the [Table 3 for the Rest/Stress group](#).

Table 2. Schedule of Activities—Dosimetry Group

| Procedure | Pre-Screen ^(a) | Screening Visit ^(b,c) | Whole-Body PET Imaging | | | Phone Follow-up ^(j) |
|---|---------------------------|----------------------------------|---|--------------------------------|--------------------------|--------------------------------|
| | | | [⁶⁸ Ga]Galmydar PET/CT ⁽ⁱ⁾ | Delayed Imaging ⁽ⁱ⁾ | Discharge ⁽ⁱ⁾ | |
| Written Informed Consent ^(b) | | X | | | | |
| Inclusion/Exclusion Criteria ^(b) | X | X | | | | |
| Adverse Events Monitoring ^(b) | | X | X | X | X | X |
| Medical Records (EHR) ^(c) | X | X | X | X | X | X |
| Demographics ^(b) | X | X | | | | |
| Medical History ^(b) | X | X | | | | |
| Concomitant Medication ^(b) | X | X | | | | X |
| Physical Exam/Evaluation ^(b) | | X | | | X | |
| Body Weight and Height ^(b) | | X | | | | |
| IV line placement ^(d) | | X | | | | |
| Clinical safety labs ^(e) | | X | X | | X | |
| Vital Signs ^(f,h,i) | | X | X | X | X | |
| 12-lead Electrocardiogram ^(h,j) | | X | X | | X | |
| Safety Monitoring ⁽ⁱ⁾ | | | X | X | | |
| Whole-Body PET/CT imaging ^(i,k) | | | X | X | | |

- a) A phone call will be conducted to determine participant interest, eligibility, and schedule study visits.
- b) Screening will occur in the CCIR facility.
- c) Safety monitoring for adverse events (AE) will occur from the time of injection to the end of participation. Participants' medical records (EHR) are followed in the event of an adverse event.
A physician or designee must evaluate participants at baseline or [⁶⁸Ga]Galmydar pre-injection and post-imaging before discharge.
- d) Two peripheral IV catheters will be placed for the [⁶⁸Ga]Galmydar injection and collection of blood samples.
- e) Blood and urine samples will be obtained for clinical safety labs (complete blood count, comprehensive metabolic panel, and urinalysis) at screening and post imaging prior to discharge. For women of child-bearing potential, a urine pregnancy test must be obtained and confirmed as negative. See [Safety Assessments](#) section.
- f) Vital signs will be obtained at screening, baseline within 5 to 15-min pre-injection and within 5 to 15-min post injection, end of first imaging session, beginning of each delayed imaging session, and prior to discharge from the imaging facility. Repeat as needed.
- g) A 12-lead ECG will be performed at screening, baseline within 60-min prior to injection, within 5 to 15-min post-injection, end of first imaging session, and prior to discharge from imaging facility. Repeat as needed.
- h) Monitoring during the PET study: Place a blood pressure cuff on the opposite arm used for the radiotracer administration to measure blood pressure and heart rate. Place electrodes on the participant's chest for continuous ECG monitoring and electrodes to obtain 12-lead ECG.
- i) Obtain a low-dose CT-AC (50 mAs) prior to the 8 mCi \pm 20% (6.4–9.6 mCi) IV injection of [⁶⁸Ga]Galmydar followed by a 10 mL saline flush. Begin whole-body PET image acquisition from the head to mid-thigh immediately post [⁶⁸Ga]Galmydar injection for 30-min and repeat at 2 hours and 4 hours.
- j) Phone follow-up will occur within 2-3 days and repeated at 5-7 days or as late as 14-days post [⁶⁸Ga]Galmydar injection. If any of the days are not business days, the follow-up phone call may occur the following business day.

Table 3. Schedule of Activities—Rest/Stress Group

| Procedure | Pre-Screen ^(a) | Screening Visit ^(b) | IMAGING DAY-1 [⁶⁸ Ga]Galmydar PET/CT ^(k) | | | IMAGING DAY-2 ¹³ N-Ammonia PET/CT ^(l) | | | Phone Follow-up ^(o) |
|--|---------------------------|--------------------------------|--|--------|--------------------------|--|--------|--------------------------|--------------------------------|
| | | | Rest | Stress | Discharge ^(m) | Rest | Stress | Discharge ^(m) | |
| Written Informed Consent | | X | | | | | | | |
| Inclusion/Exclusion Criteria | X | X | | | | | | | |
| Adverse Events ^(b) | | X | X | X | X | X | X | X | X |
| Medical Records (EHR) ^(c) | X | X | X | X | X | X | X | X | X |
| Demographics | X | X | | | X | | | | |
| Medical History ^(a,d) | X | X | | | | | | | |
| Concomitant Medication ^(b) | X | X | X | X | | X | X | | X |
| Physical Exam/Evaluation ^(d) | | X | | | | | | X | |
| Body Weight and Height ^(b) | | X | | | X | | | | |
| IV placement ^(e) | | | X | | | X | | | |
| Clinical safety labs ^(f) | | | X | X | X | | | | X |
| Vital Signs ^(g) | | | X | X | X | X | X | X | |
| 12-lead Electrocardiogram ^(h,i) | | | X | X | | X | X | | X |
| Safety Monitoring ^(g,h,i) | | | | X | X | X | X | X | |
| PET/CT imaging ^(j,k,l,m) | | | X | X | | X | X | | |

- a) A phone call will be conducted to determine participant interest, eligibility, and schedule study visits.
- b) Participants will be admitted to the Clinical and Translational Research Unit (CTRU) facility for screening, during the break between rest and stress [⁶⁸Ga]Galmydar PET, and post-imaging safety assessments before discharge.
- c) Safety monitoring for adverse events (AE) will occur from the time of injection to the end of participation. Participants' medical records are followed in the case of an adverse event.
- d) A physician or designee must evaluate participants at baseline or [⁶⁸Ga]Galmydar pre-injection and post-imaging before discharge.
- e) Two peripheral IV lines will be placed for the radiotracer injections, collection of blood samples and for the regadenoson administration during the stress PET imaging.
- f) Confirm fasting (≥ 6 hrs). Collect blood and urine samples for [⁶⁸Ga]Galmydar safety labs (complete blood count, comprehensive metabolic panel, and urinalysis) at screening, baseline, and post imaging prior to discharge from the imaging facility. For all women of childbearing potential, a urine pregnancy test must be obtained and confirmed as negative. See [Safety Assessments](#) section.
- g) Obtain vital signs at screening, baseline rest [⁶⁸Ga]Galmydar scan within 5 to 15-min pre-injection and within 5 to 15-min post injection, end of rest imaging, and prior to participant transfer to the CTRU or discharge from the imaging facility. Repeat as needed. Follow standard-of-care clinical protocol for regadenoson stress imaging scans for both radiotracers, [⁶⁸Ga]Galmydar and ¹³N-ammonia.
- h) A 12-lead ECG will be performed at screening/baseline, within 60-min prior to injection, within 5 to 15-min pre-injection, and within 5 to 15-min post injection and end of imaging prior to discharge from imaging facility. For both radiotracer stress regadenoson imaging, follow the standard-of-care clinical protocol.
- i) Monitoring: Place a blood pressure cuff on the opposite arm used for the radiotracer administration to measure blood pressure and heart rate. Place electrodes on the participant's chest for continuous ECG monitoring and electrodes to obtain 12-lead ECG.
- j) PET/CT imaging: Obtain a low-dose CT-AC (50 mAs) prior to each rest and stress radiotracer injection. If the same IV line is used for both the regadenoson and radiotracer injections, wait 10-20 sec after the normal saline flush post regadenoson injection before injecting the radiotracer.

k) [⁶⁸Ga]Galmydar Imaging Day-1:

- *Rest PET*: Administer 4 mCi ±20% (3.2–4.8 mCi) of [⁶⁸Ga]Galmydar IV injection followed by a 10 mL saline flush and immediately begin up to a 30-min list-mode data acquisition for a single bed position at the level of the heart. The interval between the rest and stress [⁶⁸Ga]Galmydar PET acquisitions *should be no less than 2 hours and no greater than 4 hours*.
- *Stress PET MPI*: Administer a rapid (10-sec) regadenoson IV injection (0.4 mg/5 mL), followed by 5 mL saline flush; 30-sec post regadenoson injection, administer 8 mCi ±20% (6.4–9.6 mCi) of [⁶⁸Ga]Galmydar IV injection followed by a 10 mL saline flush. Begin up to a 30-min list-mode data acquisition for a single bed position at the level of the heart.

l) ¹³N-Ammonia Imaging Day-2:

- *Rest PET*: Administer an IV bolus injection of 10 mCi ±20% (8–12 mCi) of ¹³N-Ammonia followed by a 10 mL saline flush and immediately begin a 10-min list-mode data acquisition (if the anterior-posterior diameter of the chest is >50cm increase to 15-min) for a single bed position at the level of the heart. The interval between the rest and stress ¹³N-ammonia acquisitions should be *no less than 1-hour*.
- *Stress PET MPI*: Administer a rapid (10-sec) regadenoson IV injection (0.4 mg/5 mL), followed by 5 mL saline flush; 30-sec post regadenoson injection, administer 10 mCi ±20% (8–12 mCi) of ¹³N-Ammonia IV bolus injection followed by a 10 mL saline flush. Begin a 10-min list-mode data acquisition (if the anterior-posterior diameter of the chest is >50cm increase to 15-min) for a single bed position at the level of the heart.

m) Transfer [⁶⁸Ga]Galmydar participants to CTRU for post imaging safety assessments and discharge.

Discharge ¹³N-Ammonia participants from the CCIR.

n) Contact [⁶⁸Ga]Galmydar participants by phone within 2-3 days post [⁶⁸Ga]Galmydar injection.

[⁶⁸Ga]Galmydar and ¹³N-ammonia imaging visits will be separated by a minimum of 3-days and not before the follow-up phone call is complete for capturing participant adverse events following the administration of [⁶⁸Ga]Galmydar. If any of the days are not business days, the phone call may occur the following business day.

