1 BACKGROUND

While exploring structure-activity relationships of organic ligands possessing an N⁴O² donor core [1-3], we identified a gallium-68-radiopharmaceutical (named herein as ⁶⁸Ga-Galmydar) that demonstrates high extraction into the myocardium of mice, rats, and rabbits while also displaying efficient clearance from the blood pool. Additionally, [⁶⁸Ga]Galmydar is recognized by MDR1 P-glycoprotein (Pgp) [4] and Breast Cancer Resistance Protein (BCRP, ABCG2) [5] as their efficient transport substrate, and thus it exploits transporter-mediated excretion pathways from the blood and liver, resulting in high heart/blood and heart/liver ratios 60-minute post injection. Live cell-imaging of rat cardiomyoblasts using Galmydar (fluorescent probe) shows its localization within the mitochondria following permeation within cells indicating excellent correlation with radiotracer uptake data [4,5]. [⁶⁸Ga]Galmydar micro positron emission tomography (PET)/computed tomography (CT) imaging of rat and rabbit hearts show high myocardial uptake and high target/background contrast. Following ligation of the left anterior descending (LAD) coronary artery in rat and rabbits, PET/CT imaging clearly showed the hypoperfused region of the left ventricle wall. These hypoperfused regions of the myocardium correlated well to the same ex vivo regions by histochemical staining post imaging. [⁶⁸Ga]Galmydar has also shown sensitivity in monitoring ischemia caused by transient ligation of LAD in rabbits on PET imaging, also with positive correlation of the ischemic region with ex vivo histology. Radiation dosimetry studies in mice extrapolated to human dosimetry estimates using Medical Internal Radiation Dosimetry (MIRD) methodology and employing FDA guidelines (21 CFR 312) of maximum allowable dose to any organ of 50 mSV indicate an allowable maximum injection dose of 8 mCi in humans. This is comparable to ¹⁸F-Flurpiridaz, another myocardial perfusion imaging (MPI) agent undergoing Phase 3 studies. Importantly, [⁶⁸Ga]Galmydar does not demonstrate any remarkable clinical pathology (toxicology) in critical organs following intravenous administration of a single dose (1000 fold excess of an IV imaging dose) of an unlabeled agent into rats over 14 days. Finally, compared to ¹³N-ammonia (a positive control), [⁶⁸Ga]Galmydar also demonstrates similar radiotracer characteristics and, in particular, comparable myocardial first pass extraction of about 70-90% so that regadenosone-induced stress myocardial perfusion and myocardial blood flow (MBF) quantification employing kinetic modeling should be comparable [6,7,8]

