5.3 Drug Administration

The Sponsor-Investigator will adhere to the procedures and requirements in accordance with applicable policies of the Radiation Safety Committee (RSC) at Washington University and the U.S. Nuclear Regulatory Commission (NRC).

A PET-certified medical professional will draw, administer, and assay the dosage in a dose calibrator before and after the administration of all radiotracers.

The Dosimetry group will receive one single intravenous administration of $8 \text{ mCi} \pm 20\%$ (6.4–9.6 mCi) of ⁶⁸Ga-Galmydar. The Rest/Stress Group will receive two intravenous administrations of ⁶⁸Ga-Galmydar, $4 \text{ mCi} \pm 20\%$ (3.2–4.8 mCi) during rest and $6 \text{ mCi} \pm 20\%$ (4.8–7.2 mCi) during the stress of [⁶⁸Ga]Galmydar on the PET MPI Imaging Day-1. The acceptable mass for each [⁶⁸Ga]Galmydar administration is $\leq 10 \text{ } \mu\text{g}$. On Imaging Day-2, subjects will receive two single intravenous administrations each of $10 \text{ mCi} \pm 20\%$ (8–12 mCi) of N-13 Ammonia.

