5.3.1 Dosage Variance

If a required administered dosage is outside the allowable range because of unforeseen circumstances, i.e., lack of radiopharmaceutical activity, an authorized user physician before administration of the tracer must approve a dosage in writing or verbally as a variance. The authorized user must provide written approval to the imaging facility within 48-hours after a verbal approval. All members of the research team will comply with the Washington University Radiation Safety Committee Policy on Dispensing of Radiopharmaceutical Dosages for Human Research Subjects.

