6 STUDY PROCEDURES

The Schedule of Activities (SoA) tables for the Dosimetry group and Rest/Stress group summarizes the study assessments and procedures, see [Attachments](#). The results of all assessments and evaluations will be recorded on the case report forms. The PI or sub-investigator delegated by the PI will review screening and evaluations to confirm eligibility criteria of all enrolled subjects. The research study team will maintain study logs, e.g., screening and enrollment logs of participants with details of screen failures, dropouts and adverse event log.

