6.4.1.2 Stress [⁶⁸Ga]Galmydar PET

- Perform all required safety assessments pre-injection of regadenoson and [⁶⁸Ga]Galmydar as described above. Monitor ECG rhythm and HR continuously during the PET scan;
- Administer a rapid (10-sec) regadenoson intravenous injection (0.4 mg/5 mL), followed by 5 mL saline flush;

- 30-sec post regadenoson injection, administer a maximum intravenous bolus injection of 6 mCi \pm 20% (4.8-7.2 mCi) with a mass of \leq 10 μ g of [⁶⁸Ga]Galmydar followed by a 10 mL normal saline flush. If the same IV line is used for both the regadenoson and radiotracer injection, wait 10 to 20 seconds after the normal saline flush post regadenoson injection before injecting the radiotracer;
- Begin up to a 30-min list-mode data acquisition for a single bed position at the level of the heart immediately post-injection;
- Perform all required safety assessments post-injection of ⁶⁸Ga-Galmydar, end of imaging and prior to discharge from the imaging facility as described above;
- Transfer participant to CTRU for post imaging assessments and procedures prior to discharge as described above.

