11.3.2.2 Rest/Stress Group

Participants will receive two [⁶⁸Ga]Galmydar intravenous administrations, 4 mCi during rest and 6 mCi during stress for the PET MPI performed on Imaging Day-1. The effective dose for a single intravenous administration of 6 mCi of [⁶⁸Ga]Galmydar is 0.62 rem and 0.41 rem for a 4 mCi administration performed. The acceptable mass of [⁶⁸Ga]Galmydar is \leq 10 μ g per administration. On Imaging Day-2, participants will receive two single administrations each of 10 mCi of ¹³N-Ammonia during the rest and stress PET MPI.

- Rest/Stress [⁶⁸Ga]Galmydar PET MPI**

The effective dose for a rest and stress PET MPI study includes an intravenous administration of 4 mCi during the rest PET and an 6 mCi administration during the stress PET MPI, and two CT-AC scans with topogram is 1.40 rem.

- Rest/Stress ¹³N-Ammonia PET MPI**

The effective dose for a single intravenous administration of 10 mCi of ¹³N-Ammonia is 0.07 rem. The effective dose for a rest/stress ¹³N-Ammonia PET MPI study includes two administrations each of 10 mCi of ¹³N-Ammonia and two CT-AC scans is 0.51 rem.

- Total Rest/Stress PET MPI**

The total effective dose for Imaging Day-1, rest/stress [⁶⁸Ga]Galmydar PET MPI and Imaging Day-2, rest/stress ¹³N-Ammonia PET MPI study is 1.91 rem. This includes one administration each of ⁶⁸Ga-Galmydar, 4.0 mCi during rest and 6 mCi during stress, and two CT-AC scans and two administrations each of 10 mCi of ¹³N-Ammonia and two CT-AC scans.

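### Table 3 gives a Galmydar stress dose of 8 mCi (6.4–9.6), but Sections 5.3 and 6.4.1.2 and the exposure figures all use 6 mCi (4.8–7.2)

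*Combined protocol and SAP*

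**What the plan says.** The stress dose of Galmydar appears in four places.

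- **Section 5.3** gives 4 mCi ±20% at rest and 6 mCi ±20% at stress. The stress range reads "4.8–7.2 mCi) during the stress of" the Galmydar study.
- **Section 6.4.1.2**, the step-by-step procedure, says to "administer a maximum intravenous bolus injection of 6 mCi", with the same 4.8–7.2 mCi range.
- **Section 11.3.2.2** works out exposure from 4 mCi plus 6 mCi. The effective dose of the 6 mCi injection "is 0.62 rem and 0.41 rem for a 4 mCi administration performed". The Galmydar day, with "an 6 mCi administration during the stress PET MPI, and two CT-AC scans with topogram is 1.40 rem". Adding the ammonia day gives 1.91 rem.
- **Section 16, Table 3 note k** says: "30-sec post regadenoson injection, administer 8 mCi ±20% (6.4–9.6 mCi) of" Galmydar.

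Two other statements bear on the conflict. Section 1 says that the mouse dosimetry, scaled to humans, results "indicate an allowable maximum injection dose of 8 mCi in humans", and Section 1.2.1 repeats that maximum. Section 6 says that the schedule "tables for the Dosimetry group and Rest/Stress group summarizes the study assessments and procedures".

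**The concern.** Table 3 is current operative text and a natural working reference on the imaging day. Someone dosing from note k would draw up 8 mCi, which Section 5.3 does not allow without a variance. Someone dosing from Section 5.3 would draw up 6 mCi, which is below note k's lower limit. No sentence says which text governs if the two differ.

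The drug is an investigational radioactive agent, and the protocol says that no human information is yet available (Sections 1.3 and 9.1). At stake are a dose above the one the body text allows, and an exposure section that would understate what participants receive. No endpoint, sample size or analysis depends on the point.

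**Working it through.** **Inputs.** From Section 11.3: Galmydar 0.103 rem/mCi, ammonia 0.007 rem/mCi, one-bed CT-AC 0.18 rem. Each imaging day has two CT-AC scans. Ammonia is given as two injections of 10 mCi.

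**Step 1: are the ranges internally correct?**
- 6 × 0.8 = 4.8 and 6 × 1.2 = 7.2 mCi.
- 8 × 0.8 = 6.4 and 8 × 1.2 = 9.6 mCi.

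Both nominal doses agree with their own ranges, so note k does not look like a garbled digit. The ranges overlap only from 6.4 to 7.2 mCi, and each nominal dose lies outside the other range (8 > 7.2; 6 < 6.4).

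**Step 2: reproduce the plan's exposure figures, then repeat with 8 mCi.**

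Injection = mCi × 0.103. Galmydar day = (4 + stress mCi) × 0.103 + 2 × 0.18. Ammonia day = 20 × 0.007 + 2 × 0.18 = 0.50 rem (stated 0.51).

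| Quantity (rem) | Stated | With 6 mCi | With 8 mCi |
|---|---|---|---|
| Stress injection | 0.62 | 6 × 0.103 = 0.618 | 8 × 0.103 = 0.824 |
| Galmydar day | 1.40 | 10 × 0.103 + 0.36 = 1.390 | 12 × 0.103 + 0.36 = 1.596 |
| Both days | 1.91 | 1.390 + 0.50 = 1.890 | 1.596 + 0.50 = 2.096 |

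With 6 mCi the stated figures come back to within 0.02 rem. The small gap could be rounding or the topogram. With 8 mCi they are missed by about 0.2 rem.

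**Step 3: size of the difference.**
- Nominal dose: 8/6 = 1.33, one third higher.
- Against the body-text ceiling: 8/7.2 = 1.11, or 11% above it.
- Added effective dose: 2 × 0.103 = 0.206 rem. That is 0.206/1.40 = 15% of the stated Galmydar day and 0.206/1.91 = 11% of the stated total.
- Top of range, one injection: 9.6 × 0.103 = 0.99 rem, against 7.2 × 0.103 = 0.74 rem.
- Against the stated maximum injection: 9.6/8 = 1.20, or 20% above it. The body-text top of 7.2 mCi is below it.

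**Step 4: which value is intended?** The rest dose in note k (4 mCi, 3.2–4.8) and the ammonia doses in note l match the body text. Only the stress dose differs, and 8 mCi (6.4–9.6) is the dosimetry group's single dose in Sections 5.3, 6.3 and 11.3.2.1 and in Table 2 note i. No section offers 8 mCi as an alternative stress dose. This suggests a copied or stale footnote, but does not prove it.

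**The case against.** The best defence is that a careful reader can settle the matter. Three sections agree on 6 mCi, the exposure figures confirm it, and Section 6 describes the tables as summaries. The added dose is small. The first two dosimetry volunteers, planned at 8 mCi, are reviewed before the rest/stress group enters (Sections 4.4 and 12). All of this stands and limits the consequence. It does not make a wrong dose in an operative table acceptable.

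Several stronger readings are tempting, and the documents do not support them.

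- *The variance rule has no defined trigger.* Section 5.3.1 applies "If a required administered dosage is outside the allowable range because of unforeseen circumstances". Because it sits under Section 5.3, the allowable range most naturally means the 4.8–7.2 mCi set there. By the same token, a rule for case-by-case exceptions does not reconcile two nominal doses.
- *The exposure arithmetic is wrong.* It is not. The figures reproduce with the dose that Section 11.3.2.2 names.
- *9.6 mCi breaches the organ-dose limit.* Section 1 ties the 8 mCi maximum to a 50 mSv organ limit, but gives no critical-organ dose per mCi. One can say only that 9.6 mCi is above the stated maximum injection, and that note k's nominal 8 mCi equals it. The comparison is per injection. The body-text day already totals 10 mCi nominally (12.0 at the top of range, against 14.4 with Table 3), so a cumulative reading would not separate the two versions.
- *The dosimetry group's 6.4–9.6 mCi range is the same error.* That range is stated consistently throughout. How an assay tolerance should sit around a nominal dose equal to the maximum is a separate operational question.
- *The dosimetry group's 2.81 and 2.87 rem rest on a miscounted number of CT-AC scans.* The 0.18 rem figure is for one bed position over the heart, and no CT-AC dose is assigned to that group, so this cannot be tested.

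**Conclusion.** The inconsistency is real and note k is wrong as written, on the reading that three sections and the exposure figures point to. Its nominal 8 mCi is 2 mCi above the body-text dose and above the 7.2 mCi ceiling. Its 9.6 mCi top is above the stated 8 mCi maximum injection. Following it would put the injection at about 0.82 rem, the Galmydar day at about 1.60 rem and the total at about 2.10 rem, so Section 11.3.2.2 would understate exposure by about 0.21 rem per participant.

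These figures assume the protocol's own unit doses, nominal activities and two CT-AC scans per day. The total remains below the 2.84 rem that Section 1.2.1 states for the dosimetry group. The case for correction rests on this being a dose instruction for an investigational radioactive drug. The documents do not show harm, and nothing in the statistical analysis is affected. That 6 mCi is the intended dose is a strong inference, which the sponsor should confirm.

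**What to change.** In Table 3 note k, change the stress dose to 6 mCi ±20% (4.8–7.2 mCi). Sections 5.3, 6.4.1.2 and 11.3.2.2 then need no change, and 0.62, 1.40 and 1.91 rem stand.

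The cost is one footnote in a protocol amendment. Design, sample size and analysis stay as they are. If the sponsor replies that 8 mCi was meant, the correction goes the other way: those three sections would need amending, the exposure restating at the figures above, and the 9.6 mCi top reconciling with the stated maximum.
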